Appendix 5. Prohibited Concomitant Medications

All prohibited drugs require a 4-week (or ≥ 5 half-lives, whichever is longer) washout, except:

* **Amiodarone** half-life averages about 58 days and requires a 290-day washout (5 half-lives).

All herbal supplements are prohibited during the study and require a 28-day washout.

** **Biologic and Non-Biologic DMARDs** which have specific washout periods listed in Appendix 1.

NOTE: Topical administration (eg, cutaneous, ophthalmic, or intravaginal) of listed concomitant medications, which are prohibited if administered systemically, is allowed in the study.	
Moderate or Potent CYP3A Inhibitors	Moderate or Potent CYP3A Inducers
HIV antivirals:	efavirenz (Sustiva)
-delavirdine (Rescriptor)	nevirapine (Viramune)
-indinavir (Crixivan)	Barbiturates
-nelfinavir (Viracept)	carbamazepine (Carbatrol, Tegretol)
-ritonavir (Kaletra, Norvir)	modafinil (Provigil)
-saquinavir (Fortovase)	phenobarbital
-atazanavir	phenytoin (Dilantin, Phenytek)
amiodarone (Cordarone, Pacerone)*	rifabutin (Mycobutin)
cimetidine (Tagamet)	rifampin (Rifadin, Rifamate, Rifater)
clarithromycin (Biaxin, Prevpac)	rifapentine (Priftin)
telithromycin (Ketek)	St. John's Wort
clotrimazole	troglitazone (Rezulin)
chloramphenicol	All Investigational Drugs
diethyl-dithiocarbamate	DMARDs
diltiazem (Cardizem, Tiazac)	All Biologics** , such as: anakinra (Kineret), etanercept (Enbrel), adalimumab (Humira), infliximab (Remicade), abatacept (Orencia), canakinumab (Ilaris), tocilizumab (Actemra), golimumab (Simponi), rituximab (Rituxan), Immunoglobulin G (IgG)
erythromycin	
fluconazole (Diflucan)	
fluvoxamine (Luvox)	
Grapefruit juice and marmalade	
itraconazole (Sporanox)	
ketoconazole (Nizoral)	Other DMARDs**: leflunomide, sulfasalazine, d-penicillamine, bucillamine, mizoribin, azathioprine, cyclosporine, tacrolimus, auranofin, aurothioglucose, aurothiomalate, staphylococcal protein A immuno-absorbant pheresis columns
mifepristone (Mifeprex, RU486)	
nefazodone (Serzone)	
norfloxacin (Shibroxin, Noroxin)	
mibefradil	
verapamil (Calan SR, Covera HS, Isoptin SR, Tarka, Verelan)	
voriconazole	

Appendix 6. Rescue Therapy

Acetaminophen/paracetamol is allowable as rescue medication if dosed no more than 10-15 mg/kg/dose orally or 15-20 mg/kg/dose rectally (not exceeding 5 doses in 24 hours) for no more than 10 consecutive days. If a subject is already taking stable background doses of acetaminophen/paracetamol, (s)he may increase the dose up to the maximum dose stated above for up to 10 consecutive days for rescue purposes.

The following paradigm should be used to determine appropriate opioid rescue therapy:

Any of the following single opioid agents may be given as rescue medication (with or without acetaminophen/paracetamol) for no more than 10 consecutive days in the following total daily doses:

Morphine	0.2-0.5 mg/kg/dose, up to 15 mg/dose. No more than 5 doses/day.
Hydromorphone (Dilaudid)	0.03-0.08 mg/kg/dose, up to 2 mg/dose. No more than 5 doses/day.
Codeine (Paveral, Tylenol #2 and #3)	0.5-1.0 mg/kg/dose, up to 60 mg/dose. No more than 5 doses a day.
Oxycodone [Roxicodone; Percocet, Tylox]	0.05-0.15 mg/kg/dose, up to 5 mg/dose. No more than 5 doses a day.

Sustained release opioid formulations (eg, OxyContin[®], MS Contin[®]) and opioids with half-lives greater than 5 hours (eg, methadone, propoxyphene) may NOT be USED for rescue medication or increased for rescue purposes.

Intravenous or intramuscular CSs, biologic response modifiers and DMARDs other than those specified as allowed DMARDs (Appendix 1) are not allowed during this study. Intra-articular CSs be given in no more than two joints, in a cumulative dose of no more than 80 mg methylprednisolone or its equivalent in any 6-month study period. Injected joints will also be considered as having their pre-injection status (tender/painful and swollen) for the remainder of the trial.

Acetaminophen/paracetamol is not permitted as a part of combination products such as over-the-counter “cold remedies” or in combination with opioids if the acetaminophen/paracetamol dose will exceed 2.6 gm/day. Subjects who require rescue for more than 10 consecutive days should be considered for allowed JIA medication adjustments or discontinued from the trial. In addition, subjects should not be dosed with rescue acetaminophen/paracetamol or opioids during the 24 hours prior to a study visit. Baseline stable acetaminophen/paracetamol or opioids should NOT be discontinued in advance of study visits.

Subjects should not be dosed with any rescue intervention within 24 hours prior to a study visit.

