3.4.1.3. Open Enrollment at the 5 mg BID Dose Level

Acceptable efficacy and safety of the 5 mg BID dose level was confirmed in the 2 cohorts at which time, enrollment was opened to additional subjects, including subjects less than 12 years old, without sJIA fever, and weighing less than 40 kg. Decisions to open enrollment at the 5 mg BID dose level were based on observed safety, systemic exposure to tofacitinib and efficacy based on the Adapted JIA ACR 30 response rate (Refer to [Section 10.3](#) for details) in the initial cohorts. The details of composition and scope of the Steering Committee is described in the Steering Committee charter.

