5.5. Administration

During the open-label phase (12 to 40 weeks), all subjects will receive active tofacitinib oral tablets or oral solution twice daily (BID) orally, approximately 12 hours (\pm 2 hours) apart, in the morning and evening, at a dosage based on the subject's body weight as specified in Table 3. In the open-label phase, subjects \geq 40 kg will receive tofacitinib 5 mg BID as oral

tablets or solution (1 mg/mL). Subjects who are unable to swallow tablets will have the option of taking oral solution. All subjects <40 kg will receive an equivalent weight-based lower dose of tofacitinib oral solution (1 mg/mL) BID as specified in Table 3. At each visit the appropriate dose will be assigned via the IRT system based on the subject's weight.

Subjects should swallow investigational product tablets whole and not manipulate or chew them prior to swallowing. Dosing cards with clear written instructions on how to properly take study medication will be provided to the subject with study medication.

Table 3. Study Treatment Dosing and Administration

Body Weight (kg)	Dosage Regimen (Run-In Phase: Tofacitinib, Double-Blind Phase: Tofacitinib/Placebo)
	5 mg BID dose level
5 - <7	2 mg (2 mL oral solution) BID
7 - <10	2.5 mg (2.5 mL oral solution) BID
10 - <15	3 mg (3 mL oral solution) BID
15 - <25	3.5 mg (3.5 mL oral solution) BID
25 - <40	4 mg (4 mL oral solution) BID
≥40	5 mg (one 5 mg tablet or 5 mL oral solution) BID

After the 12-40 weeks open-label phase, eligible subjects will proceed to the double-blind, placebo-controlled phase. They will be randomized in a 1:1 ratio to receive either active tofacitinib oral tablets/oral solution or matching placebo oral tablets/oral solution, twice daily (BID), approximately 12 hours (±2 hours) apart, in the morning and evening, at a dosage based on the subject's body weight as specified in Table 3.

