5.8.1.1. Corticosteroids (CSs)

Subjects who are treated with CSs before study start, will be allowed to continue CS treatment provided that doses are ≤ 1.0 mg/kg/day prednisone or equivalent (up to a maximum dose of 30 mg/day) and stable for at least 1 week before the first dose of tofacitinib (Day 1) throughout the full duration of Part 1 of the open-label phase.

For subjects who are receiving IV pulse CS during the Screening period, the last IV pulse should be 2 weeks prior to Baseline (Day 1) for methylprednisolone and 3 weeks prior to Baseline (Day 1) for dexamethasone. Maintenance oral CS may be started on the day following the last IV pulse. Dosing should be ≤ 1.0 mg/kg/day prednisone or equivalent (up to a maximum dose of 30 mg/day) and stable for at least 1 week prior to Baseline (Day 1).

CS use is encouraged to be tapered down to the lowest possible dose up to discontinuation during Part 2 of the open-label phase prior to entry into the double-blind randomized withdrawal phase of the study. The active CS tapering period will be up to 20 weeks in Part 2. Refer to [Section 3.2.2](#) for further details about CS tapering in Part 2. During the double-blind phase the subject must remain on a stable tapered CS dose.

For use of CS intra articular injections, please refer to Appendix 3.

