5.9. Rescue Therapy

Refer to Appendix 3 for permitted adjustments in background sJIA therapies. Permitted rescue therapy can be found in Appendix 6.

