Appendix 3. Permitted Adjustments in sJIA Therapies

The following adjustments of background medications are allowed for reasons of inadequate efficacy of current treatment, or may be tapered or discontinued due to disease improvement. Adjustments for safety reasons may be done at any time, but if this leads to changes in excess of those allowed below, the investigator must receive approval from the Pfizer project team to allow the subject to continue in the trial.

1. NSAIDs/COX-2 inhibitors: dose adjustments may be made, or background NSAID/COX-2 inhibitors may be switched, but should be no more frequently than every 3 months, and should be more than 14 days prior to a study visit.
2. Oral Corticosteroid (CS) dose should be stable for the duration of Part 1 of the open-label phase and not exceed 1.0 mg/kg/day up to 30 mg/day oral prednisone or equivalent daily. In Part 2 at each study visit if the subject continues to meet an adapted ACR 50 level of response, then the daily prednisone dose can be tapered in accordance with the tapering criteria of [Section 3.2](#). During the double-blind phase of the study the oral CS dose must remain stable unless the subject meets the flare criteria. At that time the subject will be discontinued from the study and the oral CS dose can be adjusted as necessary in the physician's judgment.
3. Methotrexate (MTX) may be administered either orally or parenterally MTX at doses not to exceed 25 mg/wk or 20 mg/m²/week (whichever is lower). The dose should be stable for at least 4 weeks before the first dose of investigational drug and remain stable for the duration of the study (open-label and double-blind phases).
4. Intra-articular steroids should be administered in a total dosage of no more than 2 mg/kg (up to 80 mg) of methylprednisolone or equivalent every 6 months. No more than two joints should be injected in any given 6-month period and individual joints should not be injected any more frequently than once in a 6-month period. **Injected joints will be considered active joints for the following 3 months.**

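### Appendix 6 caps rescue intra-articular steroid at a flat 80 mg per 6 months and omits the 2 mg/kg limit that Appendix 3 sets for the same injections

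*Protocol*

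**What the plan says.** Appendix 3 (Permitted Adjustments in sJIA Therapies), item 4, limits intra-articular steroid to an amount given "in a total dosage of no more than 2 mg/kg (up to 80 mg) of methylprednisolone or equivalent every 6 months", and adds: "No more than two joints should be injected in any given 6-month period".

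Appendix 6 (Rescue Therapy) also permits these injections in at most two joints, "in a cumulative dose of no more than 80 mg methylprednisolone or its equivalent in any 6-month study period". That sentence has no weight-based term and does not cite Appendix 3.

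Two pointers in the body lead to different appendices:

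- Section 5.8.1.1 (Corticosteroids): "For use of CS intra articular injections, please refer to Appendix 3".
- Section 5.9 (Rescue Therapy) names Appendix 3 for changes to background therapy, then says: "Permitted rescue therapy can be found in Appendix 6".

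Small children are in the trial. Section 3.4.1.3 records that "enrollment was opened to additional subjects, including subjects less than 12 years old, without sJIA fever, and weighing less than 40 kg". Section 5.5 doses the study drug by weight in this group: "All subjects <40 kg will receive an equivalent weight-based lower dose of tofacitinib oral solution". Section 5.1 sets enrolment targets of at least 12 subjects aged 2 to <6 years and at least 12 aged 6 to <12 years.

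**The concern.** The two appendices match on route, steroid equivalent, 6-month period and two-joint cap. They differ on whether body weight limits the dose. Section 5.9 divides the appendices by purpose, so a site giving an injection as rescue is directed to Appendix 6. The sentence there names joints, dose and period, and so reads as a complete rule.

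Nothing nearby signals that a per-kg limit also applies. Each of the four opioid rows in the same appendix prints a per-kg dose together with a flat cap; morphine, for example, is "0.2-0.5 mg/kg/dose, up to 15 mg/dose". The injection sentence prints only the flat cap.

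Two things are at stake. A site working from Appendix 6 could give a small child more than the weight-based limit while believing it was within protocol. And the same dose could be recorded as a deviation at a site using Appendix 3 and not at one using Appendix 6. Nothing here bears on sample size, power or alpha, and no claim is made in either direction about the flare endpoint.

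**Working it through.** **Inputs**

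- Appendix 3 item 4: 2 mg/kg, maximum 80 mg, per 6 months.
- Appendix 6: 80 mg per 6 months.
- Weight bands: Table 3 in Section 5.5.

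**Formulas**, for weight w in kg

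- Appendix 3 limit = min(2w, 80) mg
- Appendix 6 limit = 80 mg
- Ratio = 80 / min(2w, 80), which is 40/w below 40 kg and 1 at 40 kg or more
- Gap = 80 − 2w mg below 40 kg, and 0 at 40 kg or more

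**Where the printed figures agree.** 2 mg/kg × 40 kg = 80 mg. The flat figure therefore reproduces the Appendix 3 limit at 40 kg and above, and only there.

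**Illustrative weights**

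| Weight (kg) | Appendix 3 (mg) | Appendix 6 (mg) | Ratio | Gap (mg) | 80 mg as mg/kg |
|---|---|---|---|---|---|
| 10 | 20 | 80 | 4.0 | 60 | 8.0 |
| 15 | 30 | 80 | 2.67 | 50 | 5.33 |
| 20 | 40 | 80 | 2.0 | 40 | 4.0 |
| 25 | 50 | 80 | 1.6 | 30 | 3.2 |
| 30 | 60 | 80 | 1.33 | 20 | 2.67 |
| 40 | 80 | 80 | 1.0 | 0 | 2.0 |

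**By Table 3 weight band**

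- 40 kg and above: equal
- 25 to <40 kg: above 1.0 and up to 1.6 times
- 15 to <25 kg: above 1.6 and up to 2.7 times
- 10 to <15 kg: above 2.7 and up to 4.0 times

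Table 3 also has bands below 10 kg, but the eligibility criteria set no minimum weight, so I give no maximum ratio.

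**The case against.** The strongest reply is that the governing rule is already stated. Section 5.8.1.1 names this treatment, sends the reader to Appendix 3 and makes no exception for rescue. An upper bound of 80 mg does not waive a tighter bound elsewhere, so a dose within 2 mg/kg and 80 mg satisfies both texts. Section 5.8 further requires any allowed concomitant medication to be given at a locally approved, standard-of-care dose. On this view Appendix 6 is an abbreviated restatement: it also drops Appendix 3's rule that a given joint be injected at most once in 6 months. Nor does Appendix 6 always pair a per-kg dose with a flat cap, since its main acetaminophen rule is per kg only. The documents show no excess dose given and do not say whether 2 mg/kg was chosen for safety or to limit confounding.

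Much of this stands. The two rules can be satisfied together, the defect is an omission, and the ratios compare printed ceilings and not administered doses. But Section 5.9 still sends rescue use to Appendix 6, and avoiding the error there means consulting a second appendix that the injection sentence does not mention. The Section 5.8 requirement supplies no number. The missing once-per-joint rule is a further gap in the same sentence, not a reason to leave this one. No text explains why an injection given as rescue should have a looser limit than the same injection under Appendix 3.

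**Conclusion.** The concern holds. Appendix 6 is wrong as written because it omits the 2 mg/kg limit, and for every child under 40 kg its ceiling exceeds the Appendix 3 limit by a factor of 40/weight. At 40 kg and above there is no discrepancy.

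This rests on reading the two appendices as governing the same injections, which their shared route, steroid equivalent, period and joint cap support. It also assumes that Appendix 3 states the intended limit, since it carries the fuller rule and is the one Section 5.8.1.1 cites. The documents give no injection frequency or weight distribution, so the number of children affected is unknown. This is a minor safety-text correction that should be made.

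**What to change.** In the Appendix 6 sentence on intra-articular injections, replace the flat 80 mg with 2 mg/kg, up to 80 mg, of methylprednisolone or its equivalent in any 6-month study period. Classify protocol deviations against that limit at all sites. Nothing changes for subjects of 40 kg or more.

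The cost is one line in the next protocol amendment, or a clarification letter to sites; no new procedures are needed.

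One neighbouring mismatch is not settled by this change. Appendix 3 counts an injected joint as active for 3 months, while Appendix 6 keeps it at its pre-injection status for the rest of the trial. That needs its own decision.

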Appendix 7. Guidelines For Safety Monitoring And Discontinuations

The following laboratory abnormalities require prompt re-testing, ideally within 3-5 days:

- Lymphocyte counts <500 lymphocytes/mm³.
- Neutrophil counts <1000 neutrophils/mm³.
- Platelet counts <100,000 platelets/mm³.
- Any single hemoglobin value <8.0 g/dL.
- Any single hemoglobin value that is ≥ 2 gm/dL below the baseline.
- Any single AST and/or ALT elevation >3 times the upper limit of normal, regardless of the total Bilirubin (repeat laboratory testing must include CK, Total Bilirubin, Direct and Indirect Bilirubin, GGT, INR and alkaline phosphatase).
- Any single serum creatinine increase $>50\%$ over the average of screening (most recent value prior to baseline) and baseline values OR an absolute increase in serum creatinine ≥ 0.5 mg/dL (≥ 44.2 umol/L) AND any single CrCl decrease of $>30\%$ over the average of screening (most recent value prior to baseline) and baseline values.
- Increased lipid parameters (total cholesterol, LDL cholesterol, HDL cholesterol, triglycerides) should be monitored and treated according to local guidance (eg, diet and behavior modification, statin therapy).

Temporary Withholding and discontinuation of Investigational Product related to Venous Thromboembolism:

- Per Amendment 3, for subjects with suspected venous thromboembolism, investigational product treatment should be temporarily withheld while the subject is evaluated. If venous thromboembolism is confirmed, discontinue investigational product. Refer to [Section 8.2.14](#).

Investigational Product will be discontinued for:

- Serious infections (those requiring parenteral antimicrobial therapy or hospitalization), and opportunistic infections;
- Malignancies, excluding adequately treated or excised basal cell or squamous cell carcinoma of the skin and cervical carcinoma in situ;
- Confirmed venous thromboembolism;
- Two sequential lymphocyte counts <500 lymphocytes/mm³;
- Two sequential neutrophil counts <500 neutrophils/mm³;

- Two sequential platelet counts <75,000 platelets/mm³;
- Two sequential hemoglobins <8.0 g/dL or a decrease of more than 30% from baseline value;
- Two sequential AST or ALT elevations >3 times the upper limit of normal with at least one Total Bilirubin value >2 times the upper limit of normal;
- Two sequential AST or ALT elevations >3 times the upper limit of normal with an abnormal INR;
- Two sequential AST or ALT elevations >3 times the upper limit of normal accompanied by symptoms consistent with hepatic injury;
- Two sequential AST or ALT elevations >5 times the upper limit of normal, regardless of Total Bilirubin or accompanying symptoms;
- Two sequential increases in serum creatinine >50% over the average of screening and baseline values OR an absolute increase in serum creatinine ≥ 0.5 mg/dL (≥ 44.2 umol/L) over the average of screening and baseline values AND a confirmed (two sequential) CrCl decrease of >30% over the average of screening and baseline CrCl values. If the serum creatinine increase and the CrCl decrease have an identifiable and reversible reason (eg, concomitant medication), then an additional retest may be considered after discussion with the Sponsor study clinician or medical monitor. After retest, a decision for the subject to continue in the study will be made after discussion with the Sponsor study clinician or medical monitor;
- Single positive HBc Ab and a negative HBs Ab;
- Other serious or severe AEs, after consultation with the Pfizer Medical Monitor.

Appendix 8. List of Abbreviations

Abbreviation	Term
Ab	Antibody
ACR	American College of Rheumatology
AE	adverse event
ANC	Absolute neutrophil counts
ALT	alanine aminotransferase
AST	aspartate aminotransferase
BID	Twice daily
BMI	Body Mass Index
CDC	Centers for Disease Control and Prevention
CDER	Center for Drug Evaluation and Research
CDS	core data sheet
CHAQ	Childhood Health Assessment Questionnaire
CHQ	Child Health Questionnaire
COVID-19	coronavirus disease 2019
CrCl	Creatinine clearance
CRF	case report form
CRP	C-reactive protein
CS	Corticosteroids
CSA	clinical study agreement
CSF	cerebrospinal fluid
CTA	clinical trial application
CTCAE	Common Terminology Criteria for Adverse Events
DAI	dosage and administration instructions
DB	Double-blind
DMARD	Disease Modifying Antirheumatoid Drugs
DMC	data monitoring committee
DNA	deoxyribonucleic acid
DU	dispensable unit
EC	ethics committee
ECG	Electrocardiogram
EDMC	external data monitoring committee
EDP	exposure during pregnancy
EDTA	edetic acid (ethylenediaminetetraacetic acid)
eGFR	Estimated glomerular filtration rate
ELISA	Enzyme-linked immunosorbent assay
ESR	Erythrocyte Sedimentation Rate
EU	European Union
EudraCT	European Clinical Trials Database
FDA	Food and Drug Administration (United States)
FDAAA	Food and Drug Administration Amendments Act (United States)
FSH	follicle-stimulating hormone
GCP	Good Clinical Practice

Abbreviation	Term
HBV	Hepatitis B Virus
HCG	Human Chorionic Gonadotropin
HIV	human immunodeficiency virus
HCV	Hepatitis C Virus
HRQL	health-related quality of life
IB	investigator's brochure
ICH	International Council for Harmonisation of Technical Requirements for Pharmaceuticals for Human Use
ID	Identification
IgG	Immunoglobulin G
ILAR	International League Against Rheumatism
IND	investigational new drug application
INR	international normalized ratio
IOBU-SDMC	Internal Oncology Business Unit-Safety Data Monitoring Committee
IRB	institutional review board
IRC	internal review committee
IRT	interactive response technology
IUD	intrauterine device
IUS	intrauterine system
IVR	interactive voice response
IWR	interactive web response
JADAS	Juvenile Arthritis Disease Activity
JAK	Janus Kinase
JIA	Juvenile Idiopathic Arthritis
LTE	Long Term Extension (Study A3921145)
LFT	liver function test
LPD	local product document
LSLV	last subject last visit
MACE	lymphomas, major adverse cardiovascular events
MAS	Macrophage Activation Syndrome
N/A	not applicable
NMSC	non-melanoma skin cancer
OBU	Oncology Business Unit
PCD	primary completion date
PFS	pre-filled syringe
pJIA	Polyarticular Juvenile Idiopathic Arthritis
PK	Pharmacokinetics
PRCSG/PRINTO	Pediatric Rheumatology Clinical Study Group/Pediatric Rheumatology International Trials Organization
PsA	psoriatic arthritis
PT	prothrombin time
QTF-Gold	QuantiFERON®-TB Gold test
QTF-TB	QuantiFERON®-TB In-Tube test
RA	rheumatoid arthritis

Abbreviation	Term
RF+	Rheumatoid Factor positive
RF-	Rheumatoid Factor negative
RNA	ribonucleic acid
SAE	serious adverse event
SAP	statistical analysis plan
SC	Subcutaneous
SCL	Supply Chain Lead
Scr	Serum creatinine
SIB	suicidal ideation and behavior
sJIA	Systemic JIA
SOA	Schedule of Activities
SOC	Standard of Care
SOP	standard operating procedure
SPC	summary of product characteristics
SRSD	single reference safety document
SUN	Standard Uveitis Nomenclature
TB	Tuberculosis
UK	United Kingdom
ULN	upper limit of normal
US	United States
USPI	United States package insert
VTE	Venous thromboembolism
VZV	Varicella Zoster Virus

Appendix 9. The Degree of Burden and the Risk Threshold Assessment required at each visit. [article 40 (4) No. 4 of the German Medicines Act]

As written in the protocol under the [Schedule of Activities](#), in [Study Procedures](#) and [Assessments](#) sections, and here summarized, at each visit, the physician will complete the following (including, but not limited to):

1. A medical history which includes at least one conversation regarding the child's wellbeing, generally at the beginning of the study and at each visit.
2. A physical examination including vital signs, growth, and maturation.
3. Laboratory testing, eg, haematology and liver enzymes, etc.
4. Various functional and global assessments depending on the child's specific rheumatologic diagnosis such as the JIA joint assessment, CHAQ, CHQ, and the PRCG/PRINTO Disease Flare Assessment; the Physician's Global Evaluation of Overall Disease Activity.
5. The investigator also will assess for flare and ACR responses as determined by PRINTO/PRCG.
6. Adverse events such as and including blood cell numbers, liver enzyme test, renal function tests, lipid panel, evaluating for the presence of, for example, as in protocol [Section 10.7](#), serious infections, opportunistic infections, tuberculosis, herpes zoster, malignancies (excluding NMSC), non-melanoma skin cancer (NMSC), lymphomas, major adverse cardiovascular events (MACEs), interstitial lung disease, macrophage-activation syndrome (MAS), and GI perforations.

Subjects who experience a single episode of disease flare based on the JIA disease flare criteria²⁴ at any time during the study, (including the open-label run-in and double-blind phase) will be discontinued from study, and offered the possibility to continue receiving drug in the long term extension study, based on fulfilling certain safety criteria and judgement of the treating physician. Additionally, the investigator refers to Appendix 7 "Guidelines for Safety Monitoring and Discontinuations". At each visit, the investigator considers all of this and any additional information, assesses the burden of disease and the risks of continued participation, and confirms whether continued participation by the minor subject is permissible.

